**Immune Effector Cell-Associated Encephalopathy (ICE) Score**

Orientation: oriented to year, month, city, hospital: 1 point each, 4 points total				
Naming: ability to name 3 objects (e.g. clock, pen, button): 1 point each, 3 points total				
Follow Commands: can follow a simple command (e.g. show me 2 fingers): 1 point total				
Writing: can write standard sentence (e.g. Our national bird is the bald eagle): 1 point total				
Attention: can count backwards from 100 by 10: 1 point total				
Scoring				
10 = no impairment	7-9 = ICANS grade 1	3-6 = ICANS grade 2	0-2 = ICANS grade 3	0 = ICANS grade 4

ASTCT Consensus Grading for Cytokine Release Syndrome and Neurologic Toxicity Associated with Immune Effector Cells (*Biol Blood Marrow Transplant* 2019;25: 625).

**APPENDIX F: Acute GVHD Grading/Assessment**

**MAGIC CRITERIA FOR STAGING AND GRADING FOR ACUTE GVHD**

Stage	Skin (Active Erythema Only)	Liver (Bilirubin)	Upper GI	Lower GI (Stool Output/Day)	Overall Clinical Grade
0	No active (erythematous) GVHD rash	< 2 mg/dL	No or intermittent nausea, vomiting, or anorexia	Adult : < 500 mL/day or < 3 episodes day Child : < 10 mL/kg per day or < 4 episodes/day	Grade 0: No stage 1-4 of any organ
1	Maculopapular rash < 25% BSA	2-3 mg/dL	Persistent nausea, vomiting, or anorexia	Adult : 500-900 mL/day or 3-4 episodes day Child : 10-19.9 mL/kg per day or 4-6 episodes/day	Grade I: Skin Stage 1-2 (without liver, upper GI, or lower GI)
2	Maculopapular rash 25-50% BSA	3.1-6 mg/dL	-	Adult : 1000-1500 mL/day or 5-7 episodes day Child : 20-30 mL/kg per day or 7-10 episodes/day	Grade II: Stage 3 rash and/or Stage 1 liver and/or Stage 1 upper GI and/or Stage 1 lower GI
3	Maculopapular rash > 50% BSA	6.1-15 mg/dL	-	Adult : > 1500 mL/day or > 7 episodes day Child : > 30 mL/kg per day or > 10 episodes/day	Grade III: Stage 2-3 liver and/or Stage 2-3 lower GI with Stage 0-3 Skin and/or Stage 0-1 upper GI
4	Generalized erythroderma (> 50% BSA) plus bullous formation and desquamation > 5% BSA	> 15 mg/dL	-	Severe abdominal pain with or without ileus or grossly bloody stool (regardless of stool volume)	Grade IV: Stage 4 skin, liver, or lower GI with Stage 0-1 upper GI

Acute GVHD Specifications	Chronic GVHD Specifications

 
• _____ %BSA
 
• Stool Output: _____ mL/day OR _____ episodes/day.
 
• Grade: _____
 
• ECOG: _____
 
	
Does the subject have signs/symptoms of Chronic GVHD? _____
 
 
• If yes, please circle overall grade and describe: Mild / Moderate / Severe
 
• Describe: _____.
 

Signature

Date

Date of Acute GVHD staging and grading	
Skin rash extent (% of BSA)	
Skin rash stage	 Stage 0  Stage 1  Stage 2  Stage 3  Stage 4
Stool output (episodes per day)	
Stool output (estimated total volume in mL per day)	
Lower GI stage	 Stage 0  Stage 1  Stage 2  Stage 3  Stage 4
Upper GI stage	 Stage 0  Stage 1  Stage 2  Stage 3  Stage 4
Upper GI features due to GVHD	 Persistent nausea  Persistent vomiting  Persistent anorexia  None
Liver stage	 Stage 0  Stage 1  Stage 2  Stage 3  Stage 4
MAGIC Criteria Overall Clinical Grade	 Grade 0  Grade I  Grade II  Grade III  Grade IV
Did the subject experience a GVHD flare since the last visit?	 No  Yes

**APPENDIX G: Chronic GVHD Assessment (NIH Severity Score)**

	0	1	2	3
Skin Score	 No Symptoms	 <18% BSA with disease signs but NO sclerotic features	 19-50% BSA OR involvement with superficial sclerotic features “not hidebound” (able to pinch)	 >50% BSA OR deep sclerotic features “hidebound” (unable to pinch) OR impaired mobility, ulceration or severe pruritus
Mouth Score	 No symptoms	 Mild symptoms with disease signs but not limiting oral intake significantly	 Moderate symptoms with signs with partial limitation of oral intake	 Severe symptoms with disease signs on examination with major limitation of oral intake
GI Tract Score (symptoms averaged over the last 3 days)	 No symptoms	 Symptoms such as dysphagia, anorexia, nausea, vomiting, abdominal pain or diarrhea without significant weight loss (<5%)	 Symptoms associated with mild to moderate weight loss (5-15%)	 Symptoms associated with significant weight loss >15%, requires nutritional supplement for most calorie needs OR esophageal dilation
Eye Score	 No symptoms	 Mild dry eye symptoms not affecting ADL (requiring eye drops ≤3x per day) OR asymptomatic signs of keratoconjunctivitis sicca	 Moderate dry eye symptoms partially affecting ADL (requiring eye drops >3x per day or punctual plugs) WITHOUT vision impairment	 Severe dry eye symptoms significantly affecting ADL (special eyewear to relieve pain) OR unable to work because of ocular symptoms OR loss of vision caused by keratoconjunctivitis sicca
Joint and Fascia Score	 No symptoms	 Mild tightness of arms or legs, normal or mild decreased range of motion (ROM) AND not affecting ADL	 Tightness of arms or legs OR joint contractures, erythema thought due to fasciitis, moderate decrease ROM AND mild to moderate limitation of ADL	 Contracture WITH significant decrease of ROM AND significant limitation of ADL (unable to tie shoes, button shirts, dress self etc.)

Genital Tract Score <small>(score even if no GYN exam, required for men too)</small>   No GYN Exam	 No symptoms	 Symptomatic with mild distinct signs on exam AND no effect on coitus and minimal discomfort with GYN exam	 Symptomatic with distinct signs on exam AND with mild dyspareunia or discomfort with GYN exam	 Symptomatic WITH advanced signs (stricture, labia agglutination or severe ulceration) AND severe pain with coitus or inability to insert vaginal spectrum
	 Lung Score	 Mild symptoms (shortness of breath after climbing one flight of steps)	 Moderate symptoms (shortness of breath after walking on flat ground)	 Severe symptoms (shortness of breath at rest; requiring O 2 )
 Liver Score	 Normal LFTs	 Elevated bilirubin, alkaline phosphatase, AST or ALT <2x ULN	 Bilirubin > 3 mg/dl or bilirubin, AST or ALT 2-5x ULN	 Bilirubin, AST or ALT > 5x ULN

*Liver score to be completed using most recent LFTs from within +/- 2 weeks of the assessment*

Date LFT sample obtained \_\_\_\_\_

*PFT values from within one month of the assessment*

% FEV1 \_\_\_\_\_%      Date of FEV1 \_\_\_\_\_       Not done

% DLCOc \_\_\_\_\_%      Date of DLCOc \_\_\_\_\_       Not done

Is an erythematous or maculopapular rash present?       Yes       No

Does the patient have nausea, vomiting or diarrhea?       Yes       No

Date of diagnosis of cGVHD \_\_\_\_\_

Previous assessment of NIH severity grade \_\_\_\_\_

Please rate the severity of this person's chronic GVHD												
on this scale →	 None (1)			 Mild (2)			 Moderate (3)			 Severe (4)		
and on this scale → (circle one)	
cGVHD symptoms are not at all severe
 
0    1    2    3    4    5    6    7    8    9    10
 
cGVHD symptoms are most severe possible
											

## APPENDIX H: Institutional Criteria for Donor Screening

### Donor Guidelines

(adopted from Donor Screening Policy dated 5/2021, refer to this for complete guidelines)

Patients with SD/PR on their C1D28 response assessment may receive a DLI from their original donor at the discretion of the treating physician. Patients may receive cryopreserved cells from the original donation, or the previous donor must be willing to donate again. Donor selection will be in compliance with 21 CFR Part 1271 and with our institutional guidelines governing donor eligibility.

If requesting additional collections from an unrelated donor, donor assessment and consent process will occur in the apheresis center or similar donor facility. For matched related or haploidentical donors, donor assessment take place at Washington University School of Medicine. In cases where the donor medical evaluation occurred more than 6 months prior to re-donation, evaluation will be repeated per our institutional guidelines and will include the following testing:

- Complete health history and physical examination including vaccination history if greater than 6 months since original donor evaluation
- Required Tests:
  - CMP, CBC with manual differential, PT/PTT
  - HSV serology, qualitative HCG (Females of childbearing potential only)
  - BMT Donor Evaluation Test (panel includes the following tests: hepatitis B surface antigen, hepatitis C antibody, hepatitis B core total, Hep B NAT, HCV NAT, HIV NAT, WNV NAT, HIV 1-2, HTLV-I/II, *trypanosome cruzi* antibody, RPR, CMV titer. These tests must be performed by the American Red Cross).
  - Hemoglobinopathy Assessment: G-CSF mobilized, leukapheresis donors, must have a negative sickle cell test or be cleared for leukapheresis by the transplant physician.
  - ABO/Rh typing, red cell antibody screen
- All infectious disease testing must be done within seven days of an unstimulated DCI collection and within 30 days within a stimulated DCI collection
- A negative pregnancy assessment result is required within seven days prior to initiation of donor starting collection

Collection of unmobilized peripheral blood lymphocytes from donors is performed by leukopheresis. Unmanipulated donor cells are washed, counted, analyzed for viability, and cryopreserved.

## APPENDIX I: Study-Specific DSM Tables

Protocol Objectives and Subject Evaluability	
Objective	# of patients evaluable for this endpoint to date
Primary	
To evaluate the efficacy of flotetuzumab in post-allo-HCT relapsed AML and MDS following Cycle 1 of flotetuzumab (Cycle 1 Day 28 assessment).	
Secondary	
To evaluate the efficacy of flotetuzumab monotherapy in post-allo-HCT relapsed AML and MDS following Cycle 2 (or following Cycle 1 for patients that receive only one cycle).	CR and CRi at C2D28 = ORR = MLFS = PR = SD = PFS = OS =
To evaluate the safety and tolerability of flotetuzumab +/- DLI in the post-allo-HCT setting	AEs = CRS and neurotoxicity = Acute GVHD = Chronic GVHD =

Interim Analysis and Early Stopping Rules
Does the study design include an interim toxicity analysis? No
Does the study design include an interim futility analysis? Yes
If yes, please insert text describing interim futility analysis from the protocol Fifteen patients will be enrolled in the first stage. This cohort will include patients who withdraw from the study for reasons unrelated to drug toxicity. If at least 2 CR/CRi are observed out of the 15 patients, then an additional 10 patients will be enrolled. If 6 or more CR/CRi are observed at the end of study, we would conclude that there is evidence of efficacy to warrant further investigation. There is less than 5% chance to stop the trial at stage 1 if the “true” response is 30% or higher. Conversely, there will be 55% chance to terminate the study early if the true rate is only 10% or less.
If yes, please provide data from the interim futility analysis when completed:
Are there early stopping rules that outline circumstances under which the study must be suspended or closed? Yes
If yes, please insert text describing early stopping rules from the protocol A Bayesian sequential monitoring rule will be implemented for safety. The stopping rule is defined as $\Pr(\theta > \theta_T   \text{data}) > 0.8$ , where $\theta$ denotes the proportion of toxicities (as defined in Section 11.5) and $\theta_T$ denotes the expected serious toxicity rate for study treatments (set as $\theta_T = 20\%$ for non-GVHD toxicity and 25% for GVHD toxicity). Interval analyses will be performed

after every five patients has completed the first cycle of treatment (see tables below). If the accumulated observed data suggests a high chance (i.e., >80% probability) for the “true” toxicity (as defined in Section 11.5) to be >20% for non-GVHD events or 25% for GVHD events, enrollment will be paused and data for assessment of early stopping will be sent to QASMC for review to consider study termination. The following tables show the number of patients with the number of adverse events that would result in a pause of enrollment to assess premature stopping of the trial. The stopping boundaries were obtained using Multc99 version 2.1, a free-download software from M.D. Anderson Cancer Center (<https://trialdesign.org/one-page-shell.html#BTOX>). Specifically, we assume that the parameter  $\theta$  follows a prior distribution of beta (1,1), i.e.,  $\theta$  with mean = 0.5 but with relatively large variability (non-informative prior). Early stopping will be recommended if we observe 2 non-GVHD events out of the first 6 or 2 GVHD events out of first 5 patients, etc. (see Tables below), in patients treated in this trial. A simulation study is also performed to assess the operating characteristics for the above stopping rule (all scenarios are based on 10,000 simulated trials). For non-GVHD events, there will be only 15% chance to stop early if the “true” toxicity rate is 10%. In contrast, we will have 88% chance to stop early (with a median of 10 patients treated) if the “true” toxicity rate on flotetuzumab monotherapy is 30%. For GVHD events, there will be only 21% chance to stop early if the “true” rate is 15% and there will be 86% chance to stop early (with a median of 5 patients treated) if the “true” rate is 35%.

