### 5.5 Definitions of Evaluability

Endpoint	To be evaluable for this endpoint, a patient must...
Efficacy (CR and CRi, C1D28 assessment)	Have completed all Cycle 1 infusions of flotetuzumab (or discontinued treatment due to drug toxicity or disease progression). Patients who are not evaluable for the primary objective will be replaced.
Efficacy (CR and CRi, C2D28 assessment)	Have completed all Cycle 1 and 2 infusions of flotetuzumab (or discontinued treatment due to drug toxicity or disease progression) and undergone C2D28 disease assessment
Efficacy (ORR defined as PR or greater)	Have completed all Cycle 1 infusions of flotetuzumab (or discontinued treatment due to

Efficacy (MLFS rate)	drug toxicity or progression) and undergone C2D28 disease assessment (or C1D28 assessment for patients who only received Cycle 1 treatment).
Efficacy (PR rate)	
Efficacy (SD rate)	
Efficacy (PFS)	
Efficacy (OS)	Have undergone any period of infusion of flotetuzumab
Safety and tolerability (AEs by CTCAE)	
Safety and tolerability (CRS and neurotoxicity by ASTCT)	
Safety and tolerability (acute GVHD by MAGIC criteria)	
Safety and tolerability (chronic GVHD by NIH severity score)	

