### 11.5 Safety monitoring and determination of excess toxicity

To minimize risk to patients on study, we will perform interval analyses to determine if excess treatment-associated toxicity is observed during the trial. Toxicity may occur due to treatment with flotetuzumab, DLI administration, or unknown factors. Since GVHD may be an expected result of DLI, there will be separate stopping rules for excess non-GVHD toxicity and for GVHD toxicity.

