## 11.6 Stopping rules for safety

A Bayesian sequential monitoring rule will be implemented for safety. The stopping rule is defined as  $\Pr(\theta > \theta_T | \text{data}) > 0.8$ , where  $\theta$  denotes the proportion of toxicities (as defined in Section 11.5) and  $\theta_T$  denotes the expected serious toxicity rate for study treatments (set as  $\theta_T = 20\%$  for non-GVHD toxicity and  $25\%$  for GVHD toxicity). Interval analyses will be performed after every five evaluable patients (see 11.8 for patient evaluability). If the accumulated observed data suggests a high chance (i.e.,  $>80\%$  probability) for the “true” toxicity (as defined in Section 11.5) to be  $>20\%$  for non-GVHD events or  $25\%$  for GVHD events, enrollment will be paused and data for assessment of early stopping will be sent to QASMC for review to consider study termination. The following tables show the number of patients with the number of adverse events that would result in a pause of enrollment to assess premature stopping of the trial. The stopping boundaries were obtained using Multic99 version 2.1, a free-download software from M.D. Anderson Cancer Center (<https://trialdesign.org/one-page-shell.html#BTOX>). Specifically, we assume that the parameter  $\theta$  follows a prior distribution of beta (1,1), i.e.,  $\theta$  with mean = 0.5 but with relatively large variability (non-informative prior). Early stopping will be recommended if we observe 2 non-GVHD events out of the first 6 or 2 GVHD events out of first 5 patients, etc. (see Tables below), in patients treated in this trial. A simulation study is also performed to assess the operating characteristics for the above stopping rule (all scenarios are based on 10,000 simulated trials). For non-GVHD events, there will be only 15% chance to stop early if the “true” toxicity rate is 10%. In contrast, we will have 88% chance to stop early (with a median of 10 patients treated) if the “true” toxicity rate on flotetuzumab monotherapy is 30%. For GVHD events, there will be only 21% chance to stop early if the “true” rate is 15% and there will be 86% chance to stop early (with a median of 5 patients treated) if the “true” rate is 35%.

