**11.8 Analysis Populations**

Safety analysis will include all patients who receive at least one dose of treatment drug.

Efficacy analysis will include patients who complete at least 1 cycle of treatment or patients who withdraw before completing Cycle 1 for a reason at least possibly related to drug toxicity.

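### Appendix I answers No to an interim toxicity analysis and times the safety looks on Cycle 1 completers, in conflict with Sections 11.5, 11.6 and 11.8; the looks come later, but the chance of stopping is barely changed

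*Combined protocol and SAP*

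**What the plan says.** Section 11.5 commits to looks for excess toxicity: "we will perform interval analyses to determine if excess treatment-associated toxicity is observed during the trial". Section 11.6 gives the rule. The prior is beta(1,1), and enrollment pauses if the posterior probability that the toxicity rate exceeds 20% (non-GVHD) or 25% (GVHD) is above 0.8. On timing it says: "Interval analyses will be performed after every five evaluable patients (see 11.8 for patient evaluability".

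For safety, Section 11.8 reads: "Safety analysis will include all patients who receive at least one dose of treatment drug". Section 5.5 agrees, asking only that a patient "Have undergone any period of infusion of flotetuzumab".

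Appendix I holds the study-specific tables for the report that Section 12.0 sends to the QASMC. To the question "Does the study design include an interim toxicity analysis" it answers No. To the question "Are there early stopping rules that outline circumstances under which the study must be suspended or closed" it answers Yes and reproduces the Section 11.6 rule with one substantive change: looks now come "after every five patients has completed the first cycle of treatment (see tables below". The boundary tables in Section 11.6 and in Appendix I are the same, and both are headed by the number of patients treated.

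**The concern.** There are two conflicts. The first is a factual answer on an oversight form that contradicts both the protocol body and the rest of the form.

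The second is the trigger. For the primary endpoint, Section 5.5 requires that a patient "Have completed all Cycle 1 infusions of flotetuzumab (or discontinued treatment due to drug toxicity or disease progression". It therefore treats finishing Cycle 1 and stopping for toxicity as different outcomes. Under the Appendix I wording, a patient who stops for toxicity does not add to the count of five.

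The protocol's own rules link the two events. Under Table 6, a Grade 4 infusion reaction or CRS ends flotetuzumab, and Section 11.5.1 exempts only certain Grade 3 reactions from the toxicity count. Under Tables 7 and 8, Grade IV acute GVHD and severe chronic GVHD rule out restarting, and Section 11.5.2 counts both. In Cycle 1, each of these is a counted event that also holds back the next look. What is at stake is how many patients are treated before the committee examines the data.

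**Working it through.** **1. Does either Section 11.8 population support the Appendix I trigger?** No. The safety population is everyone dosed. Even the efficacy population keeps patients who leave Cycle 1 for a reason possibly related to drug toxicity. Only Appendix I leaves them out.

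**2. Which timing do the stated operating characteristics describe?** Inputs are the printed boundaries: 2, 3, 4, 5, 6 non-GVHD events and 2, 4, 5, 6, 8 GVHD events at 5, 10, 15, 20, 25 treated. Exact calculation: add a Binomial(5, p) count at each look, remove the trials that reach the boundary, and carry the rest forward.

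| Rule | True rate | Cumulative stop probability at looks 1 to 5 | Plan states |
|---|---|---|---|
| Non-GVHD | 10% | 0.081, 0.113, 0.129, 0.138, 0.143 | 15% |
| Non-GVHD | 30% | 0.472, 0.669, 0.775, 0.840, 0.882 | 88%, median 10 treated |
| GVHD | 15% | 0.165, 0.176, 0.193, 0.209, 0.211 | 21% |
| GVHD | 35% | 0.572, 0.651, 0.760, 0.838, 0.857 | 86%, median 5 treated |

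The medians also match: the cumulative probability passes one half at 10 treated for non-GVHD and at 5 for GVHD. The plan's figures therefore belong to looks every five treated patients.

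**3. When do the looks fall under Appendix I?** Let d be the share of treated patients who do not complete Cycle 1. The documents do not give d, so a range is assumed. Expected number treated at the k-th look = 5k/(1 − d). Expected completers among 25 treated = 25(1 − d).

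| d (assumed) | Look 1 | Look 2 | Look 3 | Look 4 | Look 5 | Completers of 25 |
|---|---|---|---|---|---|---|
| 0% | 5.0 | 10.0 | 15.0 | 20.0 | 25.0 | 25.0 |
| 10% | 5.6 | 11.1 | 16.7 | 22.2 | 27.8 | 22.5 |
| 20% | 6.2 | 12.5 | 18.8 | 25.0 | 31.2 | 20.0 |
| 30% | 7.1 | 14.3 | 21.4 | 28.6 | 35.7 | 17.5 |
| 40% | 8.3 | 16.7 | 25.0 | 33.3 | 41.7 | 15.0 |

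With 25 treated, the fifth look is on average out of reach from d = 10%. The fourth coincides with the last patient at 20% and is out of reach at 30%. Under Section 5.5, patients who stop for toxicity or progression are evaluable and so are not replaced.

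**4. What happens to the chance of stopping?** Non-GVHD boundaries, true rate 30%, all treated patients' events counted, at most 25 treated. The planned row is exact: mean treated = 5 × (1 + 0.528 + 0.331 + 0.225 + 0.160) = 11.2. The other rows are simulated, with toxicity as the only reason for not completing.

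| Timing | Mean treated at look 1 | Stop probability | Mean treated |
|---|---|---|---|
| Every five treated | 5.0 | 0.88 | 11.2 |
| Completers; half of those with toxicity stop early | 5.9 | 0.89 | 11.7 |
| Completers; all of those with toxicity stop early | 7.1 | 0.90 | 12.6 |

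The stop probability does not fall, because a boundary set for five patients is applied to more than five.

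**The case against.** The strongest reply is that this is a wrong tick-box and a loose phrase. The form answers Yes to stopping rules and prints the rule, the pause for QASMC review, both boundary tables, the toxicity definitions and a per-patient toxicity table. Section 9.0 has the stopping-rules form submitted continuously, and Section 12.0 has serious toxicity monitored on an ongoing basis. This stands. A reader might infer from the No that the committee is told nothing of safety monitoring, but the rest of the form shows otherwise.

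A reader might also infer that only completers' events are counted. On that reading the stop probability at 30% toxicity would fall to about 0.42 if half of the patients with toxicity stop early, and to zero if all do. The documents do not support it: Appendix I bases the decision on the accumulated data and on patients treated.

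Nor is the mismatch between boundary and number treated harmful in itself. With a beta(1,1) prior, the posterior probability that the rate exceeds 20% after x events in n patients equals Pr(Binomial(n + 1, 0.2) ≤ x). For two events this is 0.852 at n = 6 and 0.738 at n = 8, so using the boundary of 2 at a later look errs towards stopping.

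Finally, many toxicities are handled by holding and resuming the drug, non-completion also includes progression and withdrawal, and the Appendix I phrase may be an attempt at the observation window that Section 11.6 lacks. These points limit the size of the problem. They do not reconcile the two triggers, and a window can be set without leaving out patients who stop early.

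**Conclusion.** The inconsistency is real and in the current text. The No is wrong against Sections 11.5 and 11.6 and against the form itself. The completer trigger matches neither Section 11.8, nor the table headings, nor the timing behind the stated operating characteristics.

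The consequence is delay, not a weaker rule. The first look moves from 5 to about 5.6 to 8.3 treated patients. At 30% toxicity, the mean number treated rises from 11.2 to between 11.7 and 12.6. The looks tied to 20 and 25 completers may never occur. Losing the last costs little, since it comes when the planned sample is already treated; losing the one at 20 matters more.

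These sizes rest on an assumed non-completion rate of 10% to 40%, on all treated patients' events being counted, and on patients still in Cycle 1 being left out of both schedules. The case in which the 15-completer look waits for all 25 patients needs a sustained 40% and should not be taken as the expected course. The point deserves correction because it concerns when a safety rule is applied and the remedy is cheap.

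**What to change.** In Appendix I, change the answer on the interim toxicity analysis to Yes and refer to Sections 11.5 and 11.6. In Section 11.6 and Appendix I, use one trigger: a look after every five patients who received any flotetuzumab have completed or stopped Cycle 1. State that all qualifying events in treated patients count, whether or not the patient completed the cycle. This agrees with the Section 11.8 safety population and the table headings, and it supplies the missing observation window. The cost is a wording amendment to one section and one form. The boundaries, sample size and stated operating characteristics can stay as they are for this purpose.
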